STUDY PROTOCOL

Effectiveness of custom-made foot orthoses vs heel lifts in children with Calcaneal Apophysitis (Sever disease): a randomized controlled trial

Date: 04-15-2018

Scientific Background

Calcaneal apophysitis (Sever disease) is a very common ailment present in the heel of children between 7 and 15 years old (1–5). Modern literature describes calcaneal apophysitis as a syndrome caused by overuse, resulting from the production of repetitive micro-traumas (3). Mechanical etiology relates the injury to the traction forces of triceps surae and plantar fascia on the calcaneus bony surface (3–6). The anatomical unit named ACPS describes the functional connection between the Achilles tendon, the calcaneus bone and the plantar fascia (6). There, the posterior trabecular calcaneal system works as a sesamoid bone between the fascia and the tendon fibers (6). Therefore, repetitive stress of the Achilles tendon and the plantar fascia is transmitted on the calcaneus surface affecting bone remodeling: creating perpendicular fibrous bands of cartilage in the secondary ossification center of the calcaneus (7). All this, in addition to repetitive impacts on the bony surface constitutes the focus of Sever's disease (5–8).

Sever disease, fortunately, is a benign ailment which disappears without exception after puberty when the secondary ossification center of the calcaneus is closed (9). Unfortunately, nowadays no evidence-based treatments are available (10). Nevertheless, conservative ones are the most commonly used; these include: sport activity modification, stretching and strengthening exercises and the application of podiatric strategies (heel-lifts and foot orthoses) (5,9–12).

Conservative strategies described in the foregoing paragraph are widely popular (10), but present a number of handicaps. Activity cessation means an increase of sedentary lifestyle, which is a major factor in obesity (13). The prescription of “off-the-shelf” heel-lifts is very widespread (9–12). These reduce pain levels because they elevate the heel, shortening distances between the triceps surae muscle and its insertion on the calcaneus (12). Unfortunately heel-lifts do not act completely on the mechanical etiology of Sever disease: ACPS traction and repetitive impacts (3,6,8). Heel-lifts only act on Achilles tendon traction, but lose both the effect of the plantar fascia and dissipating the impacts on the bony surface of the calcaneus (8,9).

Following this line, there are some studies in literature that have used orthoses to act both on ACPS and the repetitive impacts (8,11,12,14–16). Orthoses provide support in the medial arch (relaxing plantar fascia), include a heel-lift component and a wider support surface (dispelling impacts) (8,11,12,14–16). The available evidence reported the use of orthoses (8,11,14), but most of them were prefabricated and the studies reveal statistical analysis and methodological

concerns that limit the validity of the results reported (9,16,17). Nor studies have previously compare the use of “off-the-shelf” with custom-made orthotics (16).

Objective

The present research wanted to provide a pragmatic randomized controlled trial with an intervention period of 12 weeks, with the aim to compare heel pain perception in children with calcaneal apophysitis using a custom-made Ethyl Vinyl Acetate foot orthoses and “off-the-shelf” heel lifts. Therefore, it was hypothesized that the primary outcome, pain relief, would be significantly improved with the custom-made orthosis compared to the heel lift.

Design

The study was a parallel-group, randomized controlled trial with concealed allocation, blinding of investigators and assessors and intention-to-treat analysis. It examined the effect of custom-made foot orthoses and heel lifts in children with calcaneal apophysitis. Participants were enrolled at the time of Sever disease diagnosis. After baseline assessment, children were individually randomized to “custom-made foot orthoses” (experimental group) or “off-the-self heel lifts” (control group). Concealed allocation was carried out by having randomization performed by a third party who was not involved in the recruitment and treatment of the children. Eight permuted blocks were used to stratify randomization by BMI (20 versus > 20 kg/m 2), Lunge Test (35 versus $> 35^\circ$ of dorsal flexion), FPI (4 versus > 4) and by VAS score (74 versus > 74 mm) because these were considered as important risk factors associated with pain severity in Sever disease (2,14,18,19). A researcher who was unaware of the randomized group allocation measured the outcomes at baseline and 12 weeks later. The design of the present research was based on and executed according to the CONSORT Statement. The study was approved by the Ethics Committee of Clinical Research of Aragón (C.P.-C.I.PI16/0303)

Participants

All children with Sever disease diagnosis who came for an orthopaedic treatment at Podoactiva Headquarters Podiatric Clinic between September 2015 and April 2018 were assessed for study eligibility prior treatment application. Inclusion criteria included boys and girls between 9 and 12 years old diagnosed radiologically with calcaneal osteochondritis (10). Children were excluded if they: had suffered some trauma on the heel in the past 2 months; had received anti-inflammatory drugs and/or physical treatment for pain in the past 3 months; had presented

physical or neurological impairment; or were not interested. Informed consent form with parents' and children authorization was required to be part of the study.

Interventions

Before treatment application, all children received the following information about conservative strategies for pain reduction: triceps surae stretching, sport activity intensity reduction but no cessation and 10 minutes of ice application when pain exacerbation (10).

Each intervention (custom-made foot orthoses and heel lifts), consisted of a treatment period of 12 weeks. Both interventions were prescribed, designed and fabricated by a Podiatrist expert in orthopaedics, who was unaware of the randomized group allocations.

Experimental group

Children in the experimental group received as treatment intervention custom-made polypropylene foot orthoses (Podoactiva®, Spain). They were advised pragmatically to wear the orthoses at least 8 to 10 hours per day for the daily life and during sport activity.

Control group

Children in the control group received as treatment intervention an 8 mm "off-the-shelf" heel lift (Podoactiva®, Spain). They were advised pragmatically to wear the heel lifts at least 8 to 10 hours per day for the daily life and during sport activity.

Children were blinded to group allocation. Regardless to experimental or control group they received the same attention during the consultation and they were informed that the intervention given was adequate for their disease, before treatment application and after the follow-up.

Outcome measures

All the outcomes were obtained by an experienced and trained assessor who was blinded to group allocation. At baseline participant's weight and height were measured during each session with an Año-Sayol scale and stadiometer, respectively (Año-Sayol SL, Barcelona, Spain).

The primary outcome was Sever disease pain perception, which was determined by three ways: VAS, algometry and by the following question: "Do you have pain at sport activity?" which had

to be answered by YES or NOT (Sport Activity Pain dependent variable). The VAS is commonly used to measure pain perception (20), and has been used before to measure pain perception in children with calcaneal apophysitis (14,19). The VAS is described as a horizontal line 100 mm in length where at each end points the words “No pain” and “Worst imaginable pain” are placed (18,20). Participants were asked to mark the line at the point which best represents the level of pain intensity that they were experiencing (14). Algometry is commonly used to measure pressure-pain threshold (21). To perform the algometry, the Wagner FPX™ 25 Algometer (Wagner Instruments®, USA) was used. It had been used before in children with calcaneal apophysitis (10). To perform the algometry children were asked to lie down in prone position on the stretcher, with knee and ankle bent 90°. Then the algometer was positioned on the Achilles tendon insertion on the calcaneus. Three separate measurements were obtained and the average of them was taken as algometry value (10).

Secondary outcomes were to determine the values of the FPI and the Lunge Test in the children with Sever disease. The FPI was performed following the guidelines of Redmond et al (22). FPI is a 6-point tool for clinical assessment, which evaluates the multisegmental nature of foot posture in the three spatial dimensions. Each component of the test is graded between -2 and +2 (signs of supination or pronation), where neutral is graded with 0. Finally, a score range from -12 (highly supinated) to +12 (highly pronated) is obtained (22–24). Lunge Test is commonly used to determine shortness in triceps surae muscle (2,24). Restriction in the length of this muscle is considered when the dorsal flexion of the ankle is less than 38-35° (2,5,23,24).

Statistical analysis plan

Sample size estimation was based on the detection of a difference of 29% in the number of children with pain; and a mean difference of 0.39 or superior for the algometry and the VAS, between baseline and after the follow up based on a previous pilot study (2). Assuming a two-side α of 0.05, power of 80%, and a 10% drop-out rate, a sample size of 198 participants was required. Continuous variables were expressed as mean \pm standard deviation (SD) whereas qualitative variables were expressed as frequencies and percentages. Continuous data were checked for normality by Kolmogorov-Smirnov Test.

The baseline characteristics of the children were summarized using descriptive statistics and tabulated for comparison between intervention groups. Baseline characteristics were compared between included and excluded participants to analyze whether they were representative. Mann-Whitney U and T-Student Tests were used to compare continuous variables and the Fisher Test to compare dichotomous variables.

Differences between baseline and final assessment were performed using the average-to-average method. Mann-Whitney U Test was used to compare absolute and relative changes in algometry and VAS. McNemar Test was applied to calculate the improvement, which was positive when subjects changed from pain situation to no pain situation for the dependent variable Sport Activity Pain. Identifying treatment effectiveness after the follow-up was made by regression models. Linear regression was applied to quantitative variables, algometry and VAS, and logistic regression to dichotomous qualitative variables, association was measured in terms of odds ratio.

Statistical analysis of the outcomes was performed according to intention-to-treat principles compared the groups regarding pain perception evolution. For all tests, a two-sided p-value <0.05 was considered significant. The statistical analyses were performed using the SPSS software 22.0 for Windows (SPSS Ibérica, Madrid, Spain).

REFERENCES

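### Entry does not require current pain, so relative VAS change and sport-pain improvement are not workable for any child who starts with VAS 0 or a NOT on sport pain

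*Combined protocol and SAP*

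**What the plan says.** The Objective section states the hypothesis that "the primary outcome, pain relief, would be significantly improved with the custom-made orthosis compared to the heel lift".

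The Participants section describes the source population as "All children with Sever disease diagnosis who came for an orthopaedic treatment" at the clinic. It then gives the entry rule: "Inclusion criteria included boys and girls between 9 and 12 years old diagnosed radiologically with calcaneal osteochondritis (10". The exclusions are recent heel trauma, recent drug or physical treatment for pain, physical or neurological impairment, and lack of interest. None of them concerns absence of pain.

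Under Outcome measures, "The primary outcome was Sever disease pain perception, which was determined by three ways: VAS, algometry and by the following question" about pain at sport, answered YES or NOT. The VAS asks for the pain felt at the time of marking, on a line of 100 mm.

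The Statistical analysis plan says that "Mann-Whitney U Test was used to compare absolute and relative changes in algometry and VAS". It gives no formula for relative change and no rule for a zero baseline. Improvement in sport pain is assessed with McNemar's test, "which was positive when subjects changed from pain situation to no pain situation for the dependent variable Sport Activity Pain". Linear regression (VAS, algometry) and logistic regression (dichotomous variables) are to identify treatment effectiveness. The plan does not state their exact response variables, their covariates or the set of children analysed.

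**The concern.** The trial is about pain relief, but entry rests on age and imaging. A child whose heel hurts only in sport may mark 0 mm while sitting in clinic, and a child with positive imaging may answer NOT on sport pain. Two of the planned summaries do not work for these children: a ratio to a baseline of zero, and an improvement that requires pain at the start.

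At stake is what the primary measures mean. Unless a value is assigned by hand, a child with VAS 0 falls out of the relative-change comparison, although the plan promises intention-to-treat analysis. A child with a baseline NOT can be coded in more than one way in the between-arm sport-pain analysis. The plan does not choose, so the choice could be made after the data are seen.

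**Working it through.** **The plan's sample size.** The inputs in the Statistical analysis plan are two-sided α 0.05, power 80%, 10% drop-out, a mean difference of 0.39 without unit or SD, and a 29% difference without underlying rates. The stated total is 198.

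- Means: n per arm = 2 × [(1.960 + 0.842) × SD / 0.39]². With an assumed SD of 1 this is 104, so 208 evaluable and 208 / 0.9 → 232 in total. An SD of about 0.92 to 0.93 would give 196 to 200, but the plan states no SD.
- Proportions: an absolute 29-point difference needs at most 92 evaluable, or 103 with drop-out (about 118 with continuity correction).

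The figure of 198 cannot be reproduced without added assumptions. The present point does not depend on it, but this matters for the question of power below.

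**Who can enter.** The inclusion criteria, the exclusion criteria and the VAS stratum in the Design section (cut at 74 mm, no floor) all admit a child with VAS 0 or with a baseline NOT.

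**VAS 0 at baseline.** Let b be baseline VAS and y the 12-week VAS.

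- Absolute change = y − b. With b = 0 this equals y, which is never below 0, so the best possible result is no change.
- Relative change = (y − b) / b, the usual formula (an assumption, since the plan gives none). With b = 74 and y = 0 it is −74 / 74 = −100%. With b = 0 and y = 0 it is 0 / 0, which has no value and no rank. With b = 0 and y > 0 the denominator is again zero.

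**NOT at baseline.** Improvement is a move from pain to no pain, so a child who starts without sport pain cannot show it.

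**Measure by measure.**

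| Baseline state | Absolute VAS change can show benefit | Relative VAS change defined | Can count as sport-pain improver | Algometry can improve |
|---|---|---|---|---|
| VAS > 0, YES | yes | yes | yes | yes |
| VAS 0, YES | no | no | yes | yes |
| VAS > 0, NOT | yes | yes | no | yes |
| VAS 0, NOT | no | no | no | yes |

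**What the sport-pain contrast would estimate.** Let f be the share with NOT at baseline, expected to be equal in the arms by randomisation. Let s_E and s_C be the improvement rates among baseline YES in the experimental and control arms, and r_E and r_C the shares of baseline NOT who are pain-free at 12 weeks.

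- Outcome coded as improvement, all children: (1 − f)(s_E − s_C).
- Outcome coded as pain-free at 12 weeks, all children: (1 − f)(s_E − s_C) + f(r_E − r_C).
- Improvement among baseline YES only: s_E − s_C.

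These are three different quantities whenever f > 0. The documents give no f, so the gap between them cannot be sized. If f = 0 they coincide.

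**Timing.** The Design section places randomisation after the baseline assessment. A set defined by the baseline answer is therefore fixed before allocation, and restricting to it keeps the randomised comparison.

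**The case against.** The best reply is that such children are few and the plan has other analyses. Participants were diagnosed children who came for treatment, enrolled at diagnosis, and a VAS cut at 74 mm would be odd if many scored near zero. A child with VAS 0 is lost only from the relative-change comparison, since absolute change and the regressions remain defined. McNemar's test uses only children whose answer changes, so a child who says NOT twice does not enter it. Either coding of the sport-pain outcome treats the randomised arms alike, so neither favours a device. All of this stands, and it keeps the point modest. It does not supply a zero-baseline rule or say what the logistic regression models. Seeking treatment also does not exclude a VAS of 0 on a scale that asks about pain at that moment.

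A reader might go further in three ways that the documents do not support.

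- That these children cannot improve and carry no information. The table in the working shows that algometry can improve in every row, and other measures in most rows.
- That the trial loses a calculable amount of power. The share is unknown. A share without sport pain cannot be applied to the 0.39, which belongs to VAS and algometry, has no stated SD, and is worded as a difference between baseline and follow-up. The pilot behind the planning figures may also have included such children, so a further reduction could count the same dilution twice.
- That the entry criteria must be rewritten. Recruitment ran from September 2015 to April 2018 and the protocol is dated 04-15-2018, so a new line would reach almost nobody. In a trial described as pragmatic, requiring VAS above 0 on the day could also turn away children with real activity pain who are comfortable in clinic.

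**Conclusion.** The point holds as a gap in the analysis definitions. The plan admits children with VAS 0 or a NOT on sport pain and has no rule for them in two summaries of primary pain measures. For VAS 0, relative change is undefined and absolute change cannot show benefit. For a baseline NOT, the stated improvement cannot occur.

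The size is unknown. It is zero if every child entered with VAS above 0 and a YES, and the recruitment route suggests that few were wholly pain-free. No power loss can be stated from the documents. The conclusion rests on two readings: that relative change means change divided by baseline, and that the VAS refers to pain at the visit, as Outcome measures describes it. It is still worth correcting, because the remedy uses data collected before randomisation and closes an analytic choice on primary measures.

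**What to change.** Three changes to the Statistical analysis plan:

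1. Replace the Mann-Whitney comparison of relative VAS change with a linear regression of 12-week VAS on treatment and baseline VAS, reporting the adjusted mean difference in mm with its 95% confidence interval. It is defined for every child with follow-up and gives content to the linear regression already planned. It does not create room for improvement in a child who starts at 0, but it keeps that child in the analysis.
2. Restrict the between-arm analysis of Sport Activity Pain improvement to children answering YES at baseline, and state that the logistic regression models improvement in that set.
3. Report, by arm, the number of children with VAS 0 and the number with NOT at baseline, so that readers can see how far the point matters.

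The cost is a few lines of text and no new data. The one downside is that the sport-pain improvement analysis covers a slightly smaller set, defined at baseline. No change to eligibility is proposed.

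### Must the plan's blinding statements for the podiatrist and the children be changed because no procedure is described and the two devices look different?

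*Combined protocol and SAP*

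**What the plan says.** The protocol speaks of blinding in three places.

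- **Design.** The summary promises "concealed allocation, blinding of investigators and assessors and intention-to-treat analysis". Randomization follows baseline ("After baseline assessment, children were individually randomized to" one of two devices), and concealment rests on having "randomization performed by a third party who was not involved in the recruitment and treatment of the children". The outcome assessor is described as unaware of the arm, and Outcome measures repeats this.
- **Interventions, podiatrist.** "Both interventions were prescribed, designed and fabricated by a Podiatrist expert in orthopaedics, who was unaware of the randomized group allocations".
- **Interventions, children.** "Children were blinded to group allocation". The text then says that in either arm "they received the same attention during the consultation and they were informed that the intervention given was adequate for their disease".

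The arms are defined by the device: "Children in the experimental group received as treatment intervention custom-made polypropylene foot orthoses" in one, and "Children in the control group received as treatment intervention an 8 mm" heel lift bought ready-made in the other. Both were to be worn for at least 8 to 10 hours a day.

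Outcome measures defines the primary outcome as pain perception, measured by a VAS that the child marks, a yes/no question on pain at sport, and algometry.

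**The concern.** Two statements look hard to sustain.

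First, third-party randomization conceals the next assignment from those who recruit. It does not by itself keep the person who orders and makes the device from learning the arm once the child has been assigned, and no step is described that would.

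Second, a child can see and feel whether the shoe holds a moulded orthosis or a heel lift. Equal attention and the same reassurance can hide which arm the investigators favoured, but not which device is worn.

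The Design summary adds to the doubt. It names investigators and assessors as blinded, does not define investigators, and mentions neither the children nor the podiatrist.

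At stake is the credibility of the main comparison. VAS and sport pain are the child's own answers, and a pressure-pain threshold very probably depends on the child's response too. A blinded assessor therefore does not keep the child's expectations out of the primary outcome. A reader who takes the Interventions section at face value could rate the risk of bias too low.

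**Working it through.** The plan states no figure for blinding, so there is none to reproduce. The check is mainly a reading of the sections against each other, followed by a calculation for scale.

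**Podiatrist.** The Interventions section asserts unawareness, and the Design section places randomization with someone outside recruitment and treatment. Neither describes a step that links the two. The statement is not impossible: if both devices were prepared for every child and someone else handed one over, the maker would not know the arm. The sentence says that both interventions were made by this person, and it can be read that way, although the text does not say so. The documents therefore show a missing description, not a false statement.

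**Children.** The claim is blinding to group. Nothing says that the device was masked or that the child could not identify it. The measures listed straight after the claim fit a narrower meaning: the child did not know which arm was experimental. What children were told about the other device would be in the consent text, which is not available and so cannot count against the plan.

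**Design against Interventions.** The Design list is shorter than the Interventions list. That is an omission, because no party is called blinded in one place and unblinded in the other.

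**Scale.** Inputs: 198 participants, 10% drop-out and two-sided α of 0.05, all from the Statistical analysis plan. Assumptions: equal allocation, no true effect, and every altered answer in one arm and in one direction.

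- Per arm: 198 × 0.9 / 2 = 89.1, taken as 89.
- Sport pain, unadjusted logistic regression: with a of 89 in pain in one arm and b = a − k in the other, z = [ln(a/(89−a)) − ln(b/(89−b))] / √(1/a + 1/(89−a) + 1/b + 1/(89−b)). The table gives the smallest k with p<0.05.

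| Pain, other arm | k | k/89 | k/a |
|---|---|---|---|
| 18/89 (20%) | 10 | 11% | 56% |
| 27/89 (30%) | 12 | 13% | 44% |
| 36/89 (40%) | 13 | 15% | 36% |
| 44/89 (49%) | 13 | 15% | 30% |
| 53/89 (60%) | 14 | 16% | 26% |
| 62/89 (70%) | 13 | 15% | 21% |
| 71/89 (80%) | 12 | 13% | 17% |

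Worked line: a = 44, b = 31 gives z = (−0.022 + 0.626)/0.307 = 1.97, p = 0.049. Fisher's test needs one more child in each row (11 to 15).

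- VAS: 1.96 × √(2/89) = 0.29 SD.

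The last column is the one to judge by, because only a child who would otherwise answer yes can switch to no. As a share of the whole arm (11% to 16%), the shift looks easier than it is. These figures should not be set beside the 29% in the sample-size paragraph. That paragraph words its differences as baseline to follow-up, so 29% may not be a between-arm difference. The table shows what a biased answer would have to do. It is not evidence that any answer was biased.

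**What could still change.** Recruitment ran to April 2018. If the last device was given by 30 April 2018, the 12-week visit fell 84 days later, on 23 July 2018. The reference list carries access dates of 4 and 10 April 2019, so this text was still being edited after all visits were over.

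**The case for a change.** The strongest case for a change is that it costs only words. The trial says it followed CONSORT, so a reader may fairly expect to learn who was blinded, to what and how. The hypothesis is that the custom device is superior and the primary outcome is perceived pain, which is where expectation can act. An assertion of blinding with no mechanism invites more confidence than the described design supports.

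Much of this stands. The podiatrist's unawareness has no stated procedure, the children's blinding is not said to extend to the device, and the word investigators is left open.

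What does not stand is the step from there to a needed change. Calling the trial assessor-blinded without condition would overrule a statement that may be true. Better wording would leave any expectation effect where it is. Devices this different are hard to mask, and self-report is the natural measure of perceived pain. In a trial described as pragmatic, some exposure to expectation is the price of that comparison.

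**Conclusion.** No change to the plan follows. The documents leave out detail on how the podiatrist was kept unaware and on what the children were blinded to, but they do not contradict themselves and do not claim that the worn device was concealed. Filling the gap would alter no data, no analysis and no result.

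The size and direction of any expectation bias cannot be derived from the documents. Under the stated assumptions (89 per arm, no true effect, all changes one way in one arm), 17% to 56% of the children who would report sport pain would have to answer differently to produce p<0.05, or mean VAS would have to shift by about 0.29 SD.

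The conclusion rests on reading the children's blinding as unawareness of which arm was experimental, and on the podiatrist's statement being unexplained and not disproved. A careful reader reaches the sensible position unaided: the assessor was blinded, and VAS and sport pain are self-reports open to expectation.

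### Three unranked primary pain measures are each tested at an unadjusted two-sided 0.05, and no rule says which result, or how many, would establish benefit

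*Combined protocol and SAP*

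**What the plan says.** The Objective gives a single directional hypothesis: "it was hypothesized that the primary outcome, pain relief, would be significantly improved with the custom-made orthosis" compared with the heel lift. It names no measure.

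The Outcome measures section then defines the primary outcome: "The primary outcome was Sever disease pain perception, which was determined by three ways: VAS, algometry and by the following question". The question asks whether the child has pain at sport activity and is analysed as a dichotomous variable. The three are listed without rank.

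The Statistical analysis plan says "Identifying treatment effectiveness after the follow-up was made by regression models", with linear models for algometry and VAS and logistic models for dichotomous variables. It also lists Mann-Whitney tests on absolute and on relative change in algometry and VAS, and McNemar's test for Sport Activity Pain. The significance rule is general: "For all tests, a two-sided p-value <0.05 was considered significant".

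The sample-size paragraph draws on all three measures: "Sample size estimation was based on the detection of a difference of 29% in the number of children with pain; and a mean difference"; the latter is set at 0.39 for algometry and VAS. It closes with one power figure: "power of 80%, and a 10% drop-out rate, a sample size of 198 participants was required". It does not say whether the 80% is per measure or joint.

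**The concern.** One claim depends on three measures, and the plan leaves open how three p-values become one conclusion. Two readings are possible, and they describe different trials. If any one significant measure supports the hypothesis, the 5% level applies to each test but not to the claim. If all three must be significant, the level is safe, but a power of 80% on each measure is not 80% for the trial.

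The gap matters most when the measures disagree, for example when algometry is significant and VAS is not. The plan does not say what the trial would then conclude. Without a dated rule, that choice could be made once the results are known.

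**Working it through.** **The plan's own figure.** With two-sided 0.05 and 80% power, z = 1.960 + 0.842 = 2.802.

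- 0.39 read as a standardised difference: n per arm = 2 × 2.802² / 0.39² = 103.2, so 104; total 208; 208 / 0.9 = 231.1, so 232.
- 29 percentage points between arms, least favourable case 64.5% vs 35.5%: 46 per arm; total 92; 92 / 0.9 = 102.2, so 103.

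Neither gives 198. A value near it appears only if an unstated quantity is supplied, such as an SD of about 0.93 for the 0.39, or a relative 29% reduction from about 70% (203). So 198 cannot be reproduced, but it is not shown to be wrong. The per-measure power is therefore an assumption below. With 198 × 0.9 = 178 evaluable, and 1:1 allocation assumed, there are 89 per arm.

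**Method.** There are three test statistics, each with critical value c = 1.960, and an assumed common correlation r. With U standard normal, a = √r and s = √(1 − r):

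- Any-one error, two-sided = 1 − E{[Φ((c − aU)/s) − Φ((−c − aU)/s)]³}. At r = 0 this is 1 − 0.95³ = 0.143.
- Any-one error favouring the orthosis = 1 − E{Φ((c − aU)/s)³}. At r = 0 this is 1 − 0.975³ = 0.073.
- All-three power at 80% each = E{Φ((0.842 + aU)/s)³}. At r = 0 this is 0.8³ = 0.512.
- Mixed results = P(at least one) − P(all three). At r = 0 this is 0.992 − 0.512 = 0.480.

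| Quantity | r = 0 | r = 0.5 | r = 0.9 |
|---|---|---|---|
| Any-one error, two-sided | 14.3% | 12.5% | 8.4% |
| Any-one error, favouring the orthosis (nominal 2.5%) | 7.3% | 6.3% | 4.2% |
| All-three power, 80% on each | 51% | 61% | 72% |
| All-three power, 80%, 80% and 97.7% | 63% | 68% | 75% |
| Mixed results, 80% on each | 48% | 34% | 15% |

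The 97.7% is the power for 64.5% vs 35.5% with 89 per arm, that is, the 29% read as absolute.

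**Low end of the error range.** One measure is yes/no, which weakens its correlation with the other two. Simulating individual children (89 per arm, the third measure dichotomised at 30%, 50% or 70% yes) at a latent correlation of 0.9 gives 9.4% to 10.0% two-sided and 4.7% to 5.0% favouring the orthosis.

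**Number of tests.** The table counts one test per measure. The plan also lists 2 measures × 2 kinds of change = 4 Mann-Whitney comparisons. If these could also carry the claim, the any-one error could be higher.

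**All-three error.** A joint success cannot be more probable than success on any single measure, so the error cannot exceed 5%. With no effect on any measure it is 0.01%, 0.3% and 2.3% at r = 0, 0.5 and 0.9.

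**The case against.** The strongest reply is that the sample-size sentence joins the effects with the word and, which suggests that all three were meant to succeed; there would then be no inflation. That reading is possible. But the sentence lists planning effects and is not a decision rule, and the general significance rule does not exclude a claim from a single measure.

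The second reply is that the figures rest on assumptions, and this stands. The documents give no correlations, no SD and no control rate, and they do not say that the 80% applies to each measure. Three stronger readings are therefore unsupported:

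- A reader might infer that the trial has 51% to 72% power instead of 80%. That range is not a bound. If one measure had 80% and the others nearly 100%, joint power would approach 80%. If 0.39 were an SD unit and the 29% a relative reduction from 50%, it would be about 0.74 × 0.74 × 0.50 = 27% under independence.
- A reader might infer that mixed results are to be expected even if the orthosis works as planned. At 80% per measure they occur in 15% to 48% of trials, which is substantial but always less than half.
- A reader might infer that the rule was left open on purpose or settled after the results. The header date, 15 April 2018, falls at the end of the recruitment window ("between September 2015 and April 2018 were assessed for study eligibility prior treatment application"), and the references carry April 2019 access dates, so the text may post-date the data. The documents do not show when any rule was set or who had seen what.

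**Conclusion.** The point holds. The certain defect is the missing success rule for the trial's only hypothesis, and it needs no assumption: no section supplies a ranking, composite, testing order, adjustment or any-one/all-three statement.

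The size depends on the reading. Under any-one, two-sided error is about 14% to 8%, and a false claim for the orthosis has a chance of about 7% to 4% against 2.5%, given one test per measure and correlation 0 to 0.9. Under all-three, error does not exceed 5%, but the stated 80% is not tied to that rule. Joint power cannot exceed the lowest per-measure power. It is about 51% to 72% if each measure has exactly 80%, or about 63% to 75% if the 29% is absolute and the other two measures have 80%. The plan should be corrected, since its nominal level and its power cannot be interpreted until the rule is stated.

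**What to change.** State the rule. The proposed wording has three parts:

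- One regression per measure carries the inference: 12-week value on treatment, adjusted for that measure's baseline and for the stratification factors in the Design section (BMI, Lunge Test, FPI, VAS). It is linear for VAS and algometry and logistic for Sport Activity Pain.
- Apply Holm to the three treatment p-values at two-sided family-wise 0.05. Claim benefit only for measures that pass and favour the orthosis, and report all three.
- Label the Mann-Whitney and McNemar tests as supportive, with no claim attached.

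Two alternatives are acceptable. One is to name a single primary measure and make the other two secondary. The other, if all three were intended, is to say so, keep 0.05 for each, and restate the 80% as per-measure power with the joint power beside it.

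Whichever is chosen, say when it was set. If outcome data by arm had already been seen, disclose that and report all three measures with unadjusted and Holm-adjusted p-values. Holm must not be used to relax a rule that was meant to require all three: at 80% per measure it finds at least one measure in 96%, 87% and 75% of trials at r = 0, 0.5 and 0.9, against 51%, 61% and 72% for all three.

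The cost is wording and some power. At 80% per measure, power at Holm's strictest step (0.05/3, critical value 2.394) is Φ(2.802 − 2.394) = Φ(0.408), about 66%. No extra enrolment or visits are proposed.
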